8.3 Subjects

All subjects will be dispositioned as follows:

- Screen Failure: Subject did not pass screening procedures, not called in for clinical visit;
- Candidate for enrollment: Passed screening procedures, accepts to come in for clinical visit;
- Enrolled: Subject signs informed consent and takes part in the first experimental session;
- Fitted: Subject leaves the clinic on the investigational device;
- Drop-out: Enrolled subject whose participation ended because they did not want to continue participation.
- Discontinued: Candidate for enrollment or Enrolled subject whose participation ended because they withdrew consent, were withdrawn by the Investigator, were lost to follow up, or died.

Table 6 Inclusion/Exclusion criteria

Inclusion:	Exclusion:
Only patients with the following characteristics are eligible for study entry:	Patients with the following characteristics are not eligible for study entry:
45Kg < body weight < 136Kg	Users with stump pain*
Cognitive ability to understand all instructions and questionnaires in the study;	Users with socket problems**
Unilateral TF/KD amputees that are regular prosthesis users for at least 3 months	Pregnant Users***
Current MPK users (passive MPKs only) regularly performing descent activities (stairs/ramps)	Users using Power Knee, Kenevo or mechanical knees as their prescribed prosthesis
Age \geq 18 years	Alignment that cannot be matched with the Navii setup, as described in Instructions for use.
Willing and able to participate in the study and follow the protocol	-Osseointegration

*Question on pain affecting their functional ability (yes/no)

**Socket fit: Socket fit comfort score over 5

*** Self reported

A subject can withdraw from participation at any time, at his/her discretion, and this will not have any consequences for the participant's treatment. In such cases a report stating reasons for discontinuation of the participant shall be prepared by the **LPI**. No further investigational procedures concerning the subject will be conducted, except for a statement explaining the reason for withdrawal, including but not limited to: interacting or interviewing the subject in order to obtain data on him/her; obtaining additional private information on the subject by either observing the subject or collecting or receiving such information from any source.

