The **LPI** can withdraw the participant from the trial at any time. The reasons shall be documented. There are no pre-specified criteria for discontinuation of participants from the trial. The discontinuation of participants in the trial will not result in replacement with new participants. If withdrawal is due to problems related to the investigational device the participant will be asked for permission to follow the status/condition outside the clinical investigation. The follow-up will be individualized.

Screening will be supported by Össur customers (prosthetic clinics) with potential for users fitting into the inclusion criteria.

Enrollment will take place at the Össur site in Orlando.

The total time period required to implement the clinical investigation is expected to be 12 weeks. Each individual subject is expected to participate in the clinical investigation for 4 weeks. The estimated time needed to include this number (enrolment period) is 6 weeks.

At least 10 subjects are required to finish the protocol for statistical data analysis, as specified in chapter **10.2 Sample size calculation**.

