A standardized set of questions regarding the performance of the investigational device and the subject's satisfaction will be asked as a semi-structured interview, and the responses are documented.

The activities are video recorded to visually compare the performance of the two devices.

If the user feels comfortable and safe, he will be asked to use the investigational device for 4 weeks. They will be asked to fill in a log file for e.g. use in water, use of the app, use of the locking function.

The LPI will contact the user after 2 weeks to check on any issues that may arise. The user has the option to stop the trial at any time, an appointment will be made to switch to the prescribed knee.

The second visit will be at 4 weeks after visit 1. During this visit subjects will complete the same functional tests and questionnaires as at visit 1 (excluding background information) on the investigational device. They will then be fitted back to their prescribed device and feedback will be collected.

iii) Measurements and data collection

The same questionnaires, consisting of one valid instrument (subset of PEQ questions) and device and performance specific questionnaires, will be used and filled in at two separate points in time. Background information will be collected at baseline only. An activity report will be generated from the investigational device at visit 2.

Table 7 Visit schedule and procedures

	Recruitment phase: 2-4 weeks prior to baseline	Subject visit 1: baseline	Subject visit 2: 4 weeks after visit 1
Potential subjects identified, fitting inclusion/exclusion criteria, by LPI from Össur customers		X	
LPI calls potential subjects and screens by telephone (Pain Scale, SFCS)		X	
Subject signs ICF		X	
Subject answers subset of PEQ		X	
Subject performs TUG, 2MWT and activities of daily living (Ramps, stairs, uneven terrain)		X	
Subject fills in set of questionnaires (ABC, PlusM)		X	
Subject fitted with investigational device and receives training according to training protocol		X	
Subject performs activities of daily living (Ramps, stairs, uneven terrain)		X	
Subject fills in set of questionnaires (Specific questions, comparison)		X	
Subject answers subset of PEQ		X	
Subject performs TUG, 2MWT and activities of daily living (Ramps, stairs, uneven terrain)		X	
Subject fills in set of questionnaires (ABC, PlusM)		X	
LPI prints out activity report from the investigational device/ prescribed device			X

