d) The Smart-Trial system is validated as per the Össur QMS Software Validation process PR-00037 [7] reported in VAL1825 [8]. The validation of the software system consists of review of Smart Trial company validation records. The validation of individual case report forms against the study protocol is performed by the study team and recorded.

e) In case of electronic data collection; SMART-TRIAL (www.smart-trial.com) will be used as the primary Electronic Data Capture tool in this study. SMART-TRIAL is designed and developed in compliance with the PIC/S Guidance, PI-011-3 Good Practices for Computerized Systems in Regulated "GxP" Environments, with software validation based on IEC 62304. SMART-TRIAL is designed to enable the user to comply with Good Clinical Practice (ISO 14155:2020), ICH GCP and other industry requirements, such as FDA 21 CFR Part 11 and HIPAA. f) All data in SMART-TRIAL is collected, transferred, and stored encrypted in databases, which are hosted on Microsoft Azure ISO certified servers that are managed by SMART-TRIAL within the European Union (Dublin, Ireland). Backups are performed continuously throughout the day and stored within the same server. Given that Smart-Trial does send messaging to patients in research studies, as part of the informed consent process, (as reviewed by the IRB), patients will be asked to consent to communications through these channels. Smart-Trial is adherent to CAN-SPAM and international equivalents.

g) Photographs and frames in video recordings will only contain as far as possible the lower extremities of subjects *and any ambulatory assistance provided with their hands only*. Frames containing the face or other identifiable features of subjects will be blurred, cropped or deleted if accidentally captured. The data of subjects that are withdrawn from participation will be retained. Subjects may request that their research data is delinked from their personally identifiable data during the course of the study.

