14.2 Reporting procedures

All device related adverse events will be investigated. Adverse events that are serious, unanticipated and (possibly) device related shall be reported to the sponsor by telephone as soon as possible. The complete adverse event investigation form shall be provided to the sponsor within 24 hrs via email. Within ten days the Sponsor will report to the IRB and FDA, as applicable. Any serious device related adverse event will lead to the immediate termination of the trial. In this case all participants will be contacted immediately and advised to stop using the investigational device. An appointment will be made for them to return the trial device.

Participants will be provided the contact information of the investigator and told to call them in the event of an adverse event. Furthermore, an investigator will contact them weekly to check up on any problems. The participants prescribed prosthesis will be kept at the study site while they use the investigational device. If they experience problems with the investigational device an appointment will be made with on site to investigate further.

The investigator shall supply a copy of the complete adverse event investigation form, together with a cover letter to the IRB when events are judged to be serious, unanticipated and (possibly) device related.

Contact in case of unexpected adverse event:

[name] [REDACTED]

Any device deficiencies that did not lead to an adverse event but could have led to a medical occurrence

- if either suitable action had not been taken,
- if intervention had not been made, or
- if circumstances had been less fortunate,

shall be reported according to the same procedure as if an ADE had taken place, specified above.

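### Section 8.3 gives information arising after withdrawal no stated route into the adverse event record, although section 14.2 commits to investigating every device-related event

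*Combined protocol and SAP*

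**What the plan says.** Section 14.2 commits without exception: "All device related adverse events will be investigated".

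Section 8.3 deals with withdrawal in two paragraphs.

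- **Withdrawal by the subject.** The local principal investigator (LPI) documents why: "In such cases a report stating reasons for discontinuation of the participant shall be prepared by the" LPI. Then: "No further investigational procedures concerning the subject will be conducted, except for a statement explaining the reason for withdrawal". The examples of what is barred include interviewing the subject and "obtaining additional private information on the subject by either observing the subject or collecting or receiving such information from any source".
- **Withdrawal by the LPI.** Reasons are documented, and "There are no pre-specified criteria for discontinuation of participants from the trial". The bar is not repeated here. This paragraph adds that, where the device is the cause of withdrawal, "the participant will be asked for permission to follow the status/condition outside the clinical investigation". That sentence is not limited by who made the decision.

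Section 8.4 describes the exit itself: "The user has the option to stop the trial at any time, an appointment will be made to switch to the prescribed knee". Section 13.9 covers what has already been collected: "The data of subjects that are withdrawn from participation will be retained".

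Section 14.1 defines a serious event partly by consequences that may become known only later, namely hospital admission and lasting impairment or damage.

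**The concern.** A subject may hand the knee back because of a fall or a malfunction whose consequences are not yet clear. Section 14.2 then requires the event to be investigated. Section 8.3 either forbids the study from receiving the information needed or places its collection outside the study.

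More than the completeness of the final report is at stake. Under 14.2, events that are serious, unanticipated and possibly device related go to the sponsor urgently, and from the sponsor to the IRB and FDA, as applicable, within ten days. A serious device-related event also ends the trial, and every participant is told to stop using the device. Both steps depend on seriousness being known. If seriousness emerges after exit and has no in-study path, neither step is assured, and other subjects may still be wearing the device.

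**Working it through.** The plan states no rate of device-related withdrawal and no expected event rate, so it has no figure to reproduce. The check is to follow one hypothetical event through the text: a fall judged non-serious on the day, after which the subject stops, with a hospital admission some time later.

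1. **Before exit.** Section 14.2 provides for subject-initiated calls and weekly contact. The fall is recorded, and 13.9 keeps the record. No gap.
2. **At exit.** Section 8.4 provides an appointment to return to the prescribed knee. The statement of the reason is exempt from the 8.3 bar, and the LPI reports it. No gap for the event as known that day.
3. **After exit, subject's decision, no permission for follow-up.** The bar covers interview, observation and receipt from any source. Read literally, it covers a treating clinician's report of the admission. Section 14.2 cannot be carried out.
4. **After exit, subject's decision, permission given.** Information can be obtained, but outside the investigation. No sentence links it to the adverse event form, the case report form or the investigation report.
5. **After withdrawal by the LPI because of the device.** The bar is not repeated, but the sentence on permission still places follow-up outside the investigation. The result is as in step 4. Since there are no pre-specified discontinuation criteria, the plan also does not say when a device-related exit counts as the LPI's decision rather than the subject's.
6. **Consequence.** The admission would make the event serious under 14.1. In step 3 the study may not receive that fact. In steps 4 and 5 it may be known but has no stated route into 14.2.

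**Scale.** Inputs are up to 13 enrolled (8.2) and at least 10 required to finish (8.3).

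- One event reclassified as serious after exit: 0/13 = 0% becomes 1/13 = 7.7%.
- Exits that still leave the required number of completers: 13 − 10 = 3. This counts the room available and does not predict how many will leave.

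The disposition list in 8.3 already separates a drop-out, who did not want to continue, from a discontinued subject, a category that includes withdrawal of consent. The bar and the exit text in 8.4 do not use that distinction.

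**The case against.** The best defence is that the gap is narrow. An event that prompts an exit happens before the exit, so it is recorded, retained and already within 14.2. Subjects are told to call, are contacted while on the device, and normally return to the site to be switched back. Section 8.6 makes the principal investigator and LPI responsible for investigating possible serious events, with no exception for withdrawn subjects. Section 14.2 handles deficiencies that could have caused harm as if harm had occurred. Section 14.3 assures follow-up if the whole trial stops. Ending data collection on withdrawal also protects the subject.

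Much of this stands, and it rules out three stronger readings that a reader might infer.

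- **That harmed subjects drop out of the safety record.** They do not. Only information arising after withdrawal is at risk.
- **That those who withdraw are the ones most likely to be harmed.** The documents contain no data on this.
- **That 3/13 = 23% measures the loss.** It is only the number of exits compatible with 10 completers. Treating those three as contributing nothing would raise the one-sided 95% upper bound after zero events from 1 − 0.05^(1/13) = 20.6% to 1 − 0.05^(1/10) = 25.9%. The retention rule in 13.9 contradicts that assumption.

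The bar is also written only for withdrawal by the subject.

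The defence does not supply an in-study route for information that arises after an individual withdrawal. The safeguards listed operate before exit, at exit, or when the trial as a whole ends. The responsibility in 8.6 does not say how it is to be met under the bar in 8.3.

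**Conclusion.** The point holds for information arising after withdrawal. Sections 8.3 and 14.2 cannot both be followed for a device-related event that is open when a subject chooses to leave and does not agree to follow-up. For other device-related withdrawals, follow-up takes place outside the investigation with no stated route back. The later outcome, relatedness and final seriousness of such an event can be missed, and with them the reporting and termination steps in 14.2.

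The number of affected subjects cannot be estimated from the documents. It could be none. In a trial of at most 13, though, one reclassified event is 7.7% of subjects and, under 14.2, enough to end the trial.

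The conclusion rests on a literal reading of the bar, and on the main text only. The consent form and annexes were not available and may already cover safety follow-up.

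Section 14.3 frames termination as a judgement of harm against benefit, whereas 14.2 makes it automatic. Those two sections need their own reconciliation. Either way, the decision needs to know about serious device effects.

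**What to change.** Reconcile 8.3 with 14.2 in three steps.

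- **(a)** In 8.3, and in the exit text of 8.4, distinguish a subject who stops using the device from one who withdraws consent for data collection. Keep the present bar for the second group only.
- **(b)** For subjects who stop the device, and for withdrawals by the LPI, replace the wording that puts follow-up outside the investigation. State that device-related events and deficiencies open at exit, or reported after it, are followed within the investigation. Their outcome, relatedness and seriousness are entered in the adverse event record and handled under 14.2.
- **(c)** Seek permission for this safety follow-up at enrolment, if the consent form does not already do so.

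The cost is a few sentences in the protocol, possibly one in the consent form, and a few extra contacts. Some subjects would stay open in the database beyond 4 weeks, which could delay database lock slightly. Subjects who withdraw consent keep the protection they have now.

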8.1 General

The test will be a non-randomized single group repeated measures open label prospective design with observational and self-report measures.

Amputees are a small proportion of the general population. The population group specified in the inclusion/exclusion criteria is a further subsample of amputees. For practical reasons, i.e. to achieve statistical power, it is therefore more feasible to use within-subject comparison rather than creating study arms to compare. Furthermore, as mobile amputees generally have and use a prosthetic device for their daily activities, within-comparison is feasible comparing to the subject's previous device.

All investigational activities will be conducted at the Össur Orlando site.

As stated above the primary endpoint is Satisfaction on descending stairs, see Table 5, and the secondary endpoints are satisfaction on descending ramps, balance confidence and standing comfort in that respective order of significance. In addition, there are two exploratory endpoints on mobility and balance during ambulation. See previous chapter on objectives and hypothesis and Table 5 for rationale.

Drop-outs and withdrawals will not be replaced.

Instruments for data collection will include the following:

The Prosthesis Evaluation Questionnaire (PEQ) measures prosthetic-related quality of life. It consists of 82 items grouped into nine subscales. In addition, there are individual questions not contained in the subscales regarding satisfaction, pain, transfers, prosthetic care, self-efficacy, and importance¹⁸. This study will include a set of subscales from the PEQ, including specific questions on descending activities.

TUG The Timed Up and Go (TUG) is a tool used to test basic mobility skills by asking the subject to stand up from a chair (which should not be leaned up against a wall), walk a distance of 3 meters, turn around, walk back to the chair and sit down

2MWT is a measurement of endurance that assesses walking distance over two minutes.

ABC is a Patient-reported outcome measure that asks individuals to rate how confident they are that they will not lose their balance while performing 16 different activities.

PLUS-M (Prosthetic Limb Users Survey of Mobility) is a self-report instrument for measuring mobility of adults with lower limb amputation.

Specific questionnaire: In-house generated questionnaire on specific features in the investigational device.

Log file: User should log device use and events.

Video

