8.2 Investigational Device(s) and Comparator(s)

The subjects will be asked to use the investigational device as their primary prosthesis for **4 weeks**. Individual exposure will differ between subjects. Subjects are expected to use it for their daily living activities as they would with any other prosthesis, for up to 18 hours a day depending on the amputee. The comparator device will not be used within the timeframe of the investigation. Subjects will evaluate and provide feedback on their exposure of the comparator prior to them being fitted to the investigational device.

The comparator device will be the former version Rheo Knee (XC) or any other passive microprocessor controlled prosthetic knee (excluding Kenevo as it does not have the same intended patient population as the investigational device). They have the same intended use as the investigational device. Furthermore, they are indicated for the same condition and population group. Passive MPKs are widely accepted devices, providing clinical benefits to the user.

Where possible, the subject will be using the remaining part of their current prosthetic system with the investigational device, as it was used with the comparator device. In some cases where a subject is using components from other manufacturers (e.g. feet not validated for use with the investigational device) compatible components will be provided.

No other device, medication or intervention will be used.

Up to 13 subjects are to be enrolled and therefore 13 investigational devices will be used, as the devices are intended to be used by a single patient; one for each subject.

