10.2 Sample size calculation

A convenience sample of up to 13 subjects are expected to complete the procedures.

For pass/fail criteria, see Table 4 **Endpoints, test methods and hypotheses**.

11 Amendments and Deviations from the Protocol (CIP)

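### Section 8.3 calls 10 completers required for analysis as specified in Section 10.2, but 10.2 holds only a convenience sample and no calculation, so the 10 is not a statistically derived minimum

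*Combined protocol and SAP*

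**What the plan says.** - Section 8.3: "At least 10 subjects are required to finish the protocol for statistical data analysis", followed by a reference to Section 10.2 as the place where this is specified.
- Section 10.2, headed as the sample size calculation: "A convenience sample of up to 13 subjects are expected to complete the procedures". Its only other sentence refers the reader to the table of endpoints for pass/fail criteria. The section carries no redaction mark.
- Section 8.2: "Up to 13 subjects are to be enrolled and therefore 13 investigational devices will be used". Section 8.1: "Drop-outs and withdrawals will not be replaced".
- Section 8.1, on the choice of design: "For practical reasons, i.e. to achieve statistical power, it is therefore more feasible to use within-subject comparison rather than creating study arms to compare".
- Section 10.1: the primary hypothesis is handled descriptively. B to E use mixed models with subject as a random effect.
- Section 7, Table 5 (cited in 10.1 and 10.2 as Table 4): C, D and E are met if two-minute walk distance, TUG time and PLUS-M score, respectively, do not worsen significantly. No margin is given.

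**The concern.** A reader of Section 8.3 is told that a specific number of completers is statistically required and where the justification stands. Following the reference leads to a section with no such number and no calculation.

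The gap matters because of how C to E are judged. A criterion met by the absence of a significant worsening becomes easier to meet as the sample shrinks. If 10 is believed to be a statistically adequate number, a non-significant result will be read as evidence that the new knee is no worse, when it may only reflect imprecision. Nothing in the plan tells the reader how imprecise 10 to 13 pairs would be.

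**Working it through.** **1. Can the 10 be reproduced?** No. The documents give no alpha, sidedness, power, effect size, SD, margin or drop-out rate. Working backwards, n = 10 is what a paired t-test needs for a change of 1.0 SD of the paired differences at two-sided 5% and 80% power. Inflating 10 for 20% loss gives 10/0.80 = 12.5, rounded up to 13. That could be how the numbers arose, but the plan states neither the effect size nor the loss, so it is conjecture.

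**2. Do 10 and 13 conflict?** No. With 13 enrolled and none replaced, a floor of 10 tolerates 3/13 = 23% loss.

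**3. What can 10 to 13 pairs show?**

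From the plan: n = 10 (Section 8.3) and n = 13 (Section 8.2), in a single group measured at baseline and 4 weeks. Assumed: alpha 5%, two-sided or one-sided; target power 80%; complete pairs.

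Let d be the true mean change divided by the SD of the paired differences. Two-sided power is P(T > c) + P(T < −c), where T is noncentral t with n − 1 degrees of freedom and noncentrality d√n, and c = t(0.975, n − 1). One-sided power is P(T > c) with c = t(0.95, n − 1). The 95% CI half-width, in SDs of the paired differences, is t(0.975, n − 1)/√n:

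- n = 10: 2.262/3.162 = 0.715
- n = 13: 2.179/3.606 = 0.604

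| | n = 10 | n = 13 |
|---|---|---|
| d for 80% power, two-sided | 1.00 | 0.85 |
| d for 80% power, one-sided | 0.85 | 0.73 |
| Power at d = 0.5, two-sided | 29% | 38% |
| Power at d = 0.5, one-sided | 43% | 52% |
| 95% CI half-width (SD of differences) | 0.72 | 0.60 |

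For 80% power at d = 0.5, 34 completers would be needed two-sided, or 27 one-sided.

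**4. What does this mean for C to E?** A two-sided test is non-significant whenever the 95% CI includes zero. An observed mean worsening just under 0.72 SD (n = 10) or 0.60 SD (n = 13) would therefore still meet the criterion. A true worsening of 0.5 SD would go undetected in about 71% (n = 10) or 62% (n = 13) of trials two-sided, and in 57% or 48% one-sided.

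**5. How does the scale matter?** If r is the within-subject correlation and the raw SD is equal at both visits, the SD of the differences is the raw SD × √(2(1 − r)). The two-sided detectable change at 80% power in raw-score SDs (n = 13 to n = 10) is then:

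- r = 0.5 (factor 1.00): 0.85 to 1.00
- r = 0.8 (factor 0.63): 0.54 to 0.63
- r = 0.9 (factor 0.45): 0.38 to 0.45

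The plan gives no value of r.

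**The case against.** The case for the plan is that this is a loose cross-reference in a small study that openly calls itself a convenience sample. Anyone who turns to Section 10.2 sees that the size is not power-based. The primary hypothesis has no test, so power does not apply to it. Section 8.1 describes the mobility and ambulatory balance endpoints, which match the constructs of C to E, as exploratory. The planned analysis is a mixed model, not a paired t-test, and the power figures rest on an alpha and sidedness that the plan never states. The criteria are directional, so a one-sided reading is at least as natural.

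Much of this stands. It limits the point to the tested hypotheses and requires the figures to be shown as a range under stated assumptions. The mixed-model argument changes little: with complete pairs, a random subject intercept and device condition as the only fixed effect, the test of change is essentially the paired t-test.

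Four stronger readings might be inferred, and the documents do not support them:

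- *That Section 8.1 claims the trial achieves adequate power.* It offers power as a reason to prefer paired comparison to separate arms and states no achieved level.
- *That Section 10.2 assumes no drop-out.* It gives a ceiling, which is compatible with 10, 11 or 12 completers.
- *That only very large changes are detectable.* This holds on the paired-difference scale. In raw-score SDs the detectable change could be below 0.5 if the within-subject correlation is high.
- *That a moderate loss would be missed most of the time.* For 0.5 SD this holds two-sided at both sizes, but one-sided only at n = 10.

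What the objection does not answer is that 8.3 attributes a required number to a section that does not contain it, and that C to E still carry acceptance criteria met by non-significance.

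**Conclusion.** The point holds in limited form. The minimum of 10 has no statistical basis in the documents, and the section cited for it contains no calculation. No figure is miscalculated; the fault is an unsupported attribution. A convenience sample is acceptable in itself.

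The consequence falls chiefly on C to E. Under the assumed 5% level, 10 to 13 pairs leave a 95% CI half-width of about 0.60 to 0.72 SD of the paired differences. Power against a 0.5 SD change lies between 29% and 52%, depending on sample size and sidedness. A finding of no worsening can therefore arise from imprecision alone. How serious that is on the raw-score scale depends on a within-subject correlation that the plan does not give.

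**What to change.** - **Section 8.3:** replace the statement that 10 completers are required as specified in 10.2 with a feasibility minimum of 10 completers. If the sponsor holds an actual basis for 10, put it in 10.2 and keep the reference.
- **Section 10.2:** state that this is a convenience sample, with up to 13 enrolled, at least 10 completers intended, no power calculation, and an expected 95% CI half-width of about 0.60 to 0.72 SD of the paired differences.
- **Table 5 and Section 10.1:** report C, D and E as mean paired change with a 95% CI, and say that a non-significant difference alone will not be taken as showing that the device is no worse.
- **Section 8.1:** no change is needed. The sentence on power can stay as a rationale for the within-subject design.

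The cost is wording in 8.3 and 10.2 and a change to how C to E are judged in Table 5 and 10.1. No extra subjects, visits or measurements are needed. The downside is that the stated precision, and the conclusions available for C to E, become less favourable.
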